3.5.4 Analysis Populations

For fracture endpoints a "Full-Analysis-Set" (FAS) population will be used. This will include all randomized patients, who took at least one dose of study medication, with follow-up from Randomization to study termination, without regard to protocol violations, compliance to study drug or early treatment discontinuation. Patients will be counted in the treatment group they were randomized to, irrespective of the treatment they actually received.

All available scans to determine morphometric vertebral fractures, will be used in the analyses. For morphometric fractures, a patient with no scan during the study will not be included in the FAS population. For the final analysis of clinical fractures, a calendar date (cut-off) will be determined when the pre-specified number of fracture events are seen. For the analysis of clinical fractures, patients who did not have a fracture by the time of the cut-off date will be censored at the cut-off date, unless they discontinued the study earlier, then they will be censored at the date of the last contact with the patient (either

Product: MK-0822

46

Protocol/Amendment No.: 018-04

telephone contact or study visit). Clinical fractures after the cut-off date will not be included in the analysis.

As a supportive approach, vertebral, non-vertebral and hip fracture analyses will also be performed based on the "Per-Protocol" (PP) population, to investigate the influence of missing data and protocol violators on the treatment effect. This approach excludes patients from the FAS population if they have important protocol deviations. Specific criteria to exclude a patient are identified in appendix 6.7, prior to unblinding of study database and will be based on a patient's compliance to study medication, the use of prohibited previous or concomitant medication, and the presence of secondary diagnoses which may influence the efficacy results. Data will be censored at the date of the last dose of study medication plus 30 days, for patients who did not have a clinical fracture by that time. The per-protocol analysis will not be performed if less than 10% patients (included in the FAS approach) are protocol violators.

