A similar FAS population will be used as the analysis approach for BMD endpoints and stature, including all randomized patients who took at least one dose of study medication and have the necessary on-treatment information. Missing data will be handled by the longitudinal model, therefore no imputation of missing data will be necessary. As indicated in appendix 6.7, BMD measurements taken more than 30 days after the last dose of study medication will primarily not be included in the analyses, for results to be consistent with those from phase IIb and future phase III studies. For consistency with the approach for fracture endpoints, a supportive analysis including these measurements taken long after the last dose will also be performed.

The analyses of biochemical markers of bone turnover and formation will be performed using the per-protocol approach. BMD at the total body and distal forearm and biochemical marker endpoints will only be performed for approximately 10% of the randomized patients.

Time to first major cardiovascular and cerebrovascular event will be handled similarly as clinical fractures and will be based on the FAS approach.

Summary tables for health resource and meal questionnaires and bone biopsies will be for the FAS population.

Safety analyses will be based on the "All-Patients-as-Treated" (APaT) population, which includes all randomized patients who received at least one dose of study medication. For safety analyses, patients will be included in the treatment group for the treatment they actually received. For safety analyses, missing data will not be imputed.

Product: MK-0822

47

Protocol/Amendment No.: 018-04

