Analysis of log-transformed fraction of baseline value in biochemical markers of bone resorption (s-CTX, u-NTx) and bone formation (s-BSAP, s-P1NP) will utilize the same longitudinal model as BMD endpoints. The means and the associated 95% CIs will be back-transformed for presentation and the delta method will be used to back-transform

¹ The protocol (018-00) foresaw a random intercept in the model. Due to the unstructured covariance matrix, the random intercept is redundant and therefore omitted from the model.

Product: MK-0822

50

Protocol/Amendment No.: 018-04

the between-treatment difference (in weighted LS means) and 95% confidence interval. Formal testing of treatment differences will only be performed for resorption markers. A graphical presentation of the weighted LS mean (+/-SE) change from baseline (after back-transformation) over time will also be provided, as well as a graphical presentation of the mean actual values over time by treatment. Formal testing of treatment differences will only be performed for resorption markers.

Indices of calcium and mineral homeostasis will be summarized in similar fashion to biochemical markers, and no statistical testing will be performed to compare the treatment groups.

In addition, frequency tables will be provided for the percentage of patients with 25-hydroxyvitamin D levels <9 , ≥ 9 to <20 , or ≥ 20 ng/mL at baseline and at Month 12.

Bone Biopsies

The 2-D Histomorphometry and 3-D μ -CT transilial bone biopsy measurements at Month 24 and 36 will be summarized (mean, standard error and 95% CI) for each of the treatment groups. The principle purpose of these analyses is to rule out an increased incidence of qualitative abnormalities (e.g. excessive osteoid, woven bone, mineralization defect, marrow fibrosis), the number (percent) of patients with a qualitative abnormality will therefore be summarized for both treatment groups, along with the Miettinen and Nurminen method [23] based 95% confidence interval on the difference in percentage. The incidence of qualitative abnormalities on the bone biopsies will be considered a safety endpoint rather than an efficacy endpoint.

Meal and Health Resource Utilization Questionnaires

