Patients who received medical care and type of care	Summary of number (%) of patients overall and per time point. Summary of event-rate per type of medical care visit. Summary of number (%) of patients by type of fracture.	FAS	
Meal Questionnaire			
Meal questionnaire items	Summary of number (%) of patients per time point	FAS	Only performed for “Lead Cohort”.
FAS= Full Analysis Set; PP= Per Protocol; PV= Protocol Violator [†] Incidence of qualitative abnormalities on bone biopsies will be considered a safety endpoint.			

Product: MK-0822

55

Protocol/Amendment No.: 018-04

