Month 24 to 36 (1,096)	822 to 1,186
Month 36 to 48 (1,461)	1,187 to 1,551
If the study continues beyond Year 4, additional time windows will be defined similarly. All scans within a time window will be used, not only those closest to the target day.	

Table 3

Relative Day Ranges for Efficacy Analyses
BMD and Height Endpoints

Time Point (Target Day)	Full-Analysis-Set Analysis
Baseline (1)	-90 to 7
Month 6 (183)	8 to 273 [†]
Month 12 (365)	274 to 548 [†]
Month 24 (731)	549 to 913 [†]
Month 36 (1,096)	914 to 1,278 [†]
Month 48 (1,461)	1,279 to 1,643 [†]
If the study continues beyond Year 4, additional time windows will be defined similarly. [†] Provided measurement was not more than 30 days after the last dose of treatment in the complete study. As a supportive analysis, an analysis including all data, also beyond 30 days after the last dose will also be performed.	

Product: MK-0822

28

Protocol/Amendment No.: 018-04

Table 4

Relative Day Ranges for Efficacy Analyses Biochemical
Markers of Bone Resorption and Formation and
Indices of Calcium and Mineral Homeostasis

Time Point (Target Day)	Per Protocol Analysis
Baseline (1)	-30 to 1
Month 3 (91)	49 to 133
Month 6 (183)	141 to 225
Month 9 (274)	232 to 316
Month 12 (365)	323 to 407
Month 18 (548)	506 to 590
Month 24 (731)	689 to 773
Month 30 (913)	871 to 955
Month 36 (1,096)	1,054 to 1,138
Month 42 (1,278)	1,236 to 1,320
Month 48 (1,461)	1,419 to 1,503
If the study continues beyond Year 4, additional time windows will be defined similarly. Markers and selected indices are measured at baseline, Month 6, 12, 24, 36, 48, serum calcium is measured on more timepoints.	

Table 5

Relative Day Ranges for Efficacy Analyses
Bone Biopsy Endpoints

Time Point (Target Day)	Full-Analysis-Set Analysis
End of Study or Month 36 (1,096)	≥518

Product: MK-0822

29

Protocol/Amendment No.: 018-04

Table 6

Relative Day Ranges for Efficacy Analyses
Health Resource Utilization and Meal Questionnaires

Time Point (Target Day)	Full-Analysis-Set Analysis	
	Health Resource Utilization Questionnaires	Meal Questionnaires [†]
Baseline (1)	-90 to 7	-90 to 1
Month 3 (91)	8 to 137	2 to 137 [‡]
Month 6 (183)	138 to 228	138 to 228 [‡]
Month 9 (274)	229 to 319	229 to 319 [‡]
Month 12 (365)	320 to 411	-
Month 15 (457)	412 to 502	-
Month 18 (548)	503 to 593	-
Month 21 (639)	594 to 685	-
Month 24 (731)	686 to 776	-
Month 27 (822)	777 to 867	-
Month 30 (913)	868 to 958	-
Month 33 (1,004)	959 to 1,050	-
Month 36 (1,096)	1,051 to 1,141	-

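### Qualitative bone biopsy abnormality is a safety endpoint assigned to the FAS, with no limit on time since last dose and no on-treatment analysis, so biopsies taken off drug may pull the comparison toward no difference

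*Protocol*

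**What the plan says.** Section 3.5.5.1 (Bone Biopsies) gives the aim of the biopsy analyses as to "rule out an increased incidence of qualitative abnormalities", naming excessive osteoid, woven bone, mineralization defect and marrow fibrosis as examples. The result is the number and percentage of women with an abnormality, with a Miettinen-Nurminen 95% interval for the difference. The section adds: "The incidence of qualitative abnormalities on the bone biopsies will be considered a safety endpoint rather than an efficacy endpoint". The Table 3-10 footnote repeats it ("Incidence of qualitative abnormalities on bone biopsies will be considered a safety endpoint"), and Section 3.5.5.2 says the same.

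The analysis population points the other way. Section 3.5.4: "Summary tables for health resource and meal questionnaires and bone biopsies will be for the FAS population". The Table 3-10 row for qualitative abnormality also says FAS. The FAS is defined for fractures as treated women followed to study end, "without regard to protocol violations, compliance to study drug or early treatment discontinuation". The same section puts safety analyses in APaT: "For safety analyses, patients will be included in the treatment group for the treatment they actually received".

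On timing, Appendix 6.7, Table 5, has one row, beginning "End of Study or Month 36 (1,096", with a window of day 518 onward and no last-dose footnote. For BMD, Section 3.5.4 says: "BMD measurements taken more than 30 days after the last dose of study medication will primarily not be included in the analyses", and adds a supportive analysis that includes the later scans.

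**The concern.** Sections 3.2.3.9 and 3.2.3.9.1 keep women who stop blinded therapy in follow-up. A woman who stopped at Month 12 could therefore be biopsied at Month 24 or 36, which by the Table 5 target days is 366 (731 − 365) or 731 (1,096 − 365) days after her last dose. Section 3.3.1.7 opens biopsy to consenting women at participating centers, and the only exclusion in Section 3.2.3.6.8 itself is a bleeding disorder. Under Section 3.4.1.1, women who leave therapy for excessive bone loss may be offered alendronate, so some later biopsies could reflect a different antiresorptive.

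Most efficacy comparisons lose by dilution, so the sponsor has reason to guard against it. Here the wish is to show no excess, and dilution helps that conclusion. If bone returns toward normal off drug, off-drug biopsies lower the odanacatib abnormality rate and move the whole interval toward zero. The reader would have no on-treatment result to set beside it.

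**Working it through.** The protocol gives no abnormality rate, power or off-drug share for biopsies, so there is no stated figure to reproduce. The check is first textual, then an illustration under declared assumptions.

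**1. Last-dose limits side by side**

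| Measure | Main analysis | Second analysis | Place |
|---|---|---|---|
| BMD | within 30 days of last dose | all data | 3.5.4; App. 6.7 Table 3 |
| Height | within 30 days | all data | App. 6.7 Table 3 |
| Resorption markers | within 7 days | none stated | App. 6.7 |
| Formation markers | within 30 days | none stated | App. 6.7 |
| Laboratory tests, vital signs | within 14 days | none stated | App. 6.7 Table 7 |
| Meal questionnaire | within 30 days | none stated | App. 6.7 Table 6 |
| Adverse experiences | no limit | within 91 days (Tier 1, selected Tier 2) | 3.5.5.2 |
| Bone biopsy | no limit | none stated | App. 6.7 Table 5 |

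Among these, only bone biopsy has neither a limit nor a second analysis that applies one.

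**2. Would changing FAS to APaT remove the problem?** No. Both populations take every randomized woman with at least one dose. APaT differs only in counting women by treatment received, and Appendix 6.7 keeps a woman in her randomized group after a single correct dose. The mismatch is a contradiction to reconcile; it does not itself cause dilution.

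**3. Size, if off-drug biopsies are included**

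Let f be the share of biopsied odanacatib women who are off drug, r the fraction of the excess that has reversed by biopsy, and Δ the on-drug excess. Then

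observed excess = Δ(1 − f·r).

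Assumptions, none from the protocol: 8% abnormal on odanacatib, 2% on placebo (Δ = 6.0 points), f from 10% to 30%.

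- Full reversal (r = 1): 6.0 × 0.9, 0.8, 0.7 = 5.4, 4.8, 4.2 points.
- Half reversal (r = 0.5), f = 20%: 6.0 × 0.9 = 5.4 points.
- No reversal (r = 0), or an SOP that admits only women on drug (f = 0): 6.0 points, no bias.

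**4. Chance that the interval shows the excess**

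About 200 biopsies at each of Months 24 and 36 (Section 3.3.1.7) with equal allocation is about 200 biopsies per arm in all, or 100 per arm at one time point. The number of women may be lower, because a Month 24 participant may also be biopsied at Month 36. Two-proportion normal formula, two-sided 5%:

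z = [Δ√n − 1.96√(2p̄(1 − p̄))] / √(p₁(1 − p₁) + p₂(1 − p₂)).

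At f = 0, n = 200: z = (0.8485 − 0.6041)/0.3053 = 0.80, power 78.8%. At f = 20%, p₁ = 0.068: z = (0.6788 − 0.5685)/0.2881 = 0.38, power 64.9%. Restricted to on-drug biopsies, n = 160: z = (0.7589 − 0.6041)/0.3053 = 0.51, power 69.4%.

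| f (r = 1) | Excess, all biopsies | Power, all (200 per arm) | Power, on drug only | Power, all (100 per arm) | Power, on drug only |
|---|---|---|---|---|---|
| 0 | 6.0 | 78.8% | 78.8% | 49.5% | 49.5% |
| 10% | 5.4 | 72.5% | 74.5% | 43.8% | 45.5% |
| 20% | 4.8 | 64.9% | 69.4% | 37.9% | 41.3% |
| 30% | 4.2 | 56.3% | 63.6% | 32.1% | 36.9% |

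The restricted analysis assumes the same share off drug in both arms. It keeps the full 6.0 points and, despite fewer biopsies, slightly more power.

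**5. Upper confidence limits (Miettinen-Nurminen)**

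- All biopsies at f = 20%, rounded counts, 14/200 v 4/200: 1.0 to 9.7 points.
- On drug only, 13/160 v 3/160: 1.7 to 11.8 points.
- No dilution at full size, 16/200 v 4/200: 1.9 to 10.8 points.

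The gap of 2.1 points (11.8 − 9.7) is not all dilution: 1.0 of it (11.8 − 10.8) comes from the smaller sample and rounded counts.

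**The case against.** The strongest reply is that an unrestricted main analysis fits this trial. Appendix 6.7 describes a pure intention-to-treat study. The primary adverse-experience analysis, which includes adjudicated osteonecrosis of the jaw and delayed fracture union, runs irrespective of compliance, and the fracture and cardiovascular main analyses have no limit either. A reader might infer from the table above that every comparable measure is confined to time on drug; that is not so. Restricting to women still on drug also has a cost, because it removes women who may have stopped for tolerability, and that selection can itself bias a harm comparison. This stands, and it is why the on-treatment analysis should sit beside the all-biopsy analysis rather than replace it.

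The second reply is the biopsy SOP. Sections 3.2.3.6.8 and 3.3.1.7 leave further inclusion requirements and details of the procedure and analysis to an SOP that is not shown. It may already confine biopsy to women on drug. This also stands and makes the concern conditional. A separate SAP is a weaker answer: Section 3.5 says the protocol incorporates the SAP's details, and Appendix 6.7 exists so that no separate document is needed. Table 5 is where the biopsy window is fixed.

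Third, reversal is not established. Section 1.3 speaks of rapid clearance of odanacatib from bone compared with bisphosphonates, which makes reversal plausible but says nothing about histology.

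Finally, no exclusion margin is stated, so no declared threshold would be wrongly met.

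**Conclusion.** Two things are established from the text. The population for qualitative biopsy abnormality contradicts its status as a safety endpoint. And the biopsy analysis has neither a last-dose limit nor an on-treatment companion, although its purpose is to rule out harm and women off drug remain in the study.

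The bias is a risk of known direction, not a demonstrated fact. A reader might infer that abnormal bone on odanacatib will be diluted, or that the FAS assignment dilutes it. The documents support neither: the off-drug share and the degree of reversal are not given, the SOP is not shown, and APaT would admit the same women. Under the assumed 8% v 2% with full reversal, the excess would fall from 6.0 to between 5.4 and 4.2 points for 10% to 30% off drug. With no reversal, or no off-drug biopsies, it would not fall at all. This is a cheap improvement rather than a serious flaw.

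**What to change.** - In Section 3.5.4 and Table 3-10, assign qualitative biopsy abnormality to APaT, in line with its status as a safety endpoint.
- In Section 3.5.4, Table 3-10 and Table 5, add a pre-specified analysis of biopsies taken within a stated interval of the last dose of blinded therapy, reported beside the all-biopsy analysis. The 91 days already used for adverse experiences is one candidate. Set the interval before unblinding, so that it cannot look chosen from the data.
- Tabulate time since last dose at biopsy by arm, so that a reader can see whether dilution was possible.
- While Table 5 is open, give Month 24 its own row; biopsies are planned then, but the table has only the one open window.

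The cost is protocol wording, one extra analysis table and the short tabulation, with fewer biopsies in the restricted analysis. No new data collection is needed, provided dose and biopsy dates are recorded. If the SOP already limits biopsy to women on drug, the two analyses will agree and nothing is lost.

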3.5.5 Statistical Methods

3.5.5.1 Efficacy Analyses

Morphometric Vertebral Fractures

Life-table estimates of the proportion of patients with at least one fracture will be provided for the Month 6 time point and each of the yearly time points, as well as an estimate of the treatment difference and its 95% confidence interval (CI). In the definition of the life-table estimates a patient who does not have a scan at a timepoint (nor later), defined by the time windows in appendix 6.7, will be considered to be censored immediately after the previous time point, since no additional information on the presence/absence of a fracture is available for this patient after the last available scan.

An interval-censored survival approach will be used to evaluate the treatment effect [21; 22]. A generalized linear model for binary data will therefore be used with the complementary log-log transformation of the probability of an event up to the time point, including all available data from the regularly scheduled x-rays. The model will include terms for treatment, stratum (prior/no prior fracture), and geographic region. An estimate of the hazard ratio from the model will be provided along with its 95% confidence interval. The validity of the proportional hazards assumption will be explored (e.g. using the life-table estimates or by investigation of a similar model with treatment-time point interaction added to the model). Consistency of the treatment effect across strata and regions will also be investigated by summary statistics. These analyses and tables will consider only the first fracture per patient. The number (percent) of patients with at least one new morphometric vertebral fracture on the 6-month and yearly x-rays will also be summarized, for each of the treatment groups.

A sensitivity analysis will be performed in treated patients who received at least one dose of double-blind treatment and did not have any on-treatment lateral spine radiographs, and who are therefore excluded from the primary analysis described above. In this group of patients, the fracture rate will be assumed to be equal to that observed in the placebo group of the patients with spine radiograph (primary analysis). This approach conservatively assumes that there is no treatment effect in the group of patients without on-treatment radiograph. The hazard ratio comparing the two treatment groups (placebo and odanacatib) among patients without a spine radiograph will be combined using meta-analytical methods with the hazard ratio among the patients with radiograph. This will provide an overall estimate of the hazard ratio and 95% confidence interval for all patients (both with and without radiograph) and will allow us to investigate the effect of excluding patients without radiographs from the primary analysis.

Summaries will also be provided in the subgroup of bisphosphonate-intolerant patients (defined as patients with a contraindication or history of intolerance to bisphosphonates, or those considered by their physician to be unsuitable for bisphosphonate treatment).

Product: MK-0822

48

Protocol/Amendment No.: 018-04

The proportion of patients with at least one fracture during the first 3 years of the treatment period and the treatment difference, will be estimated using the life-table method.

In addition to these analyses of the first vertebral fracture, a summary will also be provided for the number (percent) of patients with 0, 1, 2, or more than 2 fractures up to Month 6 and each of the yearly time points.

Non-Vertebral, Hip and Clinical Vertebral Fractures

For non-vertebral, hip and clinical vertebral fractures, since the exact date of the fracture is available in the database, the data will be analyzed using continuous time-to-event methodologies. Kaplan-Meier estimates of the cumulative incidence of first fracture at different time points will be provided, as well as an estimate of the treatment difference and its 95% CI, and the data will be graphically summarized with Kaplan-Meier plots. Treatments will be compared using a Cox Proportional Hazard model with terms for treatment, stratum, and geographic region. Model-based estimates of the hazard ratio, and its 95% confidence interval, will be provided. The validity of the proportional hazards assumption will be explored (e.g. by investigation of similar models with treatment-time or treatment-log(time) interaction added). Consistency of the treatment effect across strata and regions will also be investigated by Kaplan-Meier or hazard ratio estimates within stratum/region.

The proportion of patients with at least one fracture during the first 3 years of the treatment period and the treatment difference, will be estimated using the Kaplan-Meier method.

In addition to these analyses of the first fracture, a summary will also be provided for the number (percent) of patients with 0, 1, 2, more than 2 fractures up to Month 6 and each of the yearly time points.

As a sensitivity analysis, similar analyses will be performed for all adjudicated clinical hip fractures, irrespective if they were osteoporotic (defined as fractures that occur in the absence of trauma or in a low impact trauma setting that would not have resulted in fracture in an individual *without* osteoporosis), traumatic (i.e., secondary to excessive force capable of causing a fracture in an individual *without* osteoporosis), stress or pathological. A similar sensitivity analysis will also be performed for all adjudicated non-vertebral, adjudicated vertebral and all adjudicated fractures.

Stature

The mean (and standard error [SE]) baseline and follow-up height, as well as the mean and 95% CI on the change from baseline will be tabulated for each of the treatment groups and yearly time points.

A graphical presentation of the mean (+/-SE) change from baseline in stature over time will also be provided.

Product: MK-0822

49

Protocol/Amendment No.: 018-04

In addition, the percentage of patients who experienced a stature loss of greater than 1 cm during the study will be tabulated. A logistic model will be used to compare the two treatment groups, including terms for treatment, geographic region and stratum. The model-based odds ratio, and 95% confidence interval, will be provided as an estimate of the treatment effect.

The rate of stature loss will also be examined, using a mixed model with fixed effects for treatment, geographic region, stratum, treatment-year interaction and random intercept and slope (year). The within patient serial correlation of the values over time will be modeled by an unstructured covariance matrix. The magnitude of the slopes (rate of stature loss) will be summarized from the model, as well as the difference between treatments (mean and 95% CI). More detail on this mixed model is in appendix 6.7.

Bone Mineral Density Endpoints

For each body site and timepoint, BMD will be summarized at baseline and follow-up, by the mean and standard error, together with the mean percent change from baseline and its 95% confidence interval.

The percent change from baseline in BMD endpoints at all during-treatment time points will be analyzed using a longitudinal model with fixed effects for treatment, stratum, geographic region, and treatment-by-time interaction¹. The within patient serial correlation of the values over time will be modeled by an unstructured covariance matrix. More detail on this longitudinal model is in appendix 6.7.

The treatment effect at each of the on-treatment time points will be assessed by evaluating the within- and between-treatment group Least-Squares means (LS mean) and the associated 95% confidence intervals. Treatment difference will be tested at each of the on-treatment time points and adjustment for multiple testing will be handled as discussed below.

Similar analyses will be performed in the subgroup of bisphosphonate-intolerant patients (defined as patients with a contraindication or history of intolerance to bisphosphonates, or those considered by their physician to be unsuitable for bisphosphonate treatment).

A graphical presentation of the LS mean (+/-SE) change from baseline over time will also be provided.

Biochemical Markers

Analysis of log-transformed fraction of baseline value in biochemical markers of bone resorption (s-CTX, u-NTx) and bone formation (s-BSAP, s-P1NP) will utilize the same longitudinal model as BMD endpoints. The means and the associated 95% CIs will be back-transformed for presentation and the delta method will be used to back-transform

¹ The protocol (018-00) foresaw a random intercept in the model. Due to the unstructured covariance matrix, the random intercept is redundant and therefore omitted from the model.

Product: MK-0822

50

Protocol/Amendment No.: 018-04

the between-treatment difference (in weighted LS means) and 95% confidence interval. Formal testing of treatment differences will only be performed for resorption markers. A graphical presentation of the weighted LS mean (+/-SE) change from baseline (after back-transformation) over time will also be provided, as well as a graphical presentation of the mean actual values over time by treatment. Formal testing of treatment differences will only be performed for resorption markers.

Indices of calcium and mineral homeostasis will be summarized in similar fashion to biochemical markers, and no statistical testing will be performed to compare the treatment groups.

In addition, frequency tables will be provided for the percentage of patients with 25-hydroxyvitamin D levels <9 , ≥ 9 to <20 , or ≥ 20 ng/mL at baseline and at Month 12.

Bone Biopsies

The 2-D Histomorphometry and 3-D μ -CT transilial bone biopsy measurements at Month 24 and 36 will be summarized (mean, standard error and 95% CI) for each of the treatment groups. The principle purpose of these analyses is to rule out an increased incidence of qualitative abnormalities (e.g. excessive osteoid, woven bone, mineralization defect, marrow fibrosis), the number (percent) of patients with a qualitative abnormality will therefore be summarized for both treatment groups, along with the Miettinen and Nurminen method [23] based 95% confidence interval on the difference in percentage. The incidence of qualitative abnormalities on the bone biopsies will be considered a safety endpoint rather than an efficacy endpoint.

Meal and Health Resource Utilization Questionnaires

Results of the health resource utilization questionnaire will be summarized at each of the during treatment time points and overall, by means of number (%) of patients who received medical care for a fracture since the last visit and the number (%) patients who received each of the types of medical care (physician or other healthcare professional office, emergency room visit, hospital admission, nursing home or rehabilitation hospital admission, physical therapy clinic visit).

In addition, although originally not foreseen in the protocol, event rates for each type of medical care visit will also be summarized overall and by time point for each treatment group, for all types of visits combined and by type of medical care visit. The event rate will be calculated as the number of patients with at least one medical care visit (per type) divided by the number of patient-years of follow-up.

Furthermore, the number and percent of patients who experienced each type of medical care by fracture type will also be summarized.

Results of the meal questionnaire will be summarized at Months 3, 6, and 9, for the patients of the "Lead Cohort".

Product: MK-0822

51

Protocol/Amendment No.: 018-04**Major Cardiovascular and Cerebrovascular Events**

Time to first major cardiovascular and cerebrovascular event will be summarized in tabular and graphical format by the Kaplan-Meier method and estimation of the hazard ratio.

Population PK

Population PK analysis and/or PK/PD modeling may be performed. Details will be specified in a separate population PK/PD Statistical Analysis Plan.

Genetic Markers

The purpose of the proposed genetic analyses will be to identify those genetic markers or genotypes that associate with osteoporotic end points within two frameworks: (1) treatment with odanacatib and (2) treatment with placebo. Each consenting patient's genetic material will be genotyped to determine if specific genes are shared by all patients who display a progression of the disease, and/or a reverse based upon intervention. The specific goals are three-fold. First, to identify novel genes that are causal drivers of osteoporosis and can be used as potential targets for future intervention; second, to identify loci that predict disease and disease course; and third, to identify genes/proteins that can be utilized as biomarkers in downstream musculoskeletal studies to reflect a patient's likelihood to respond favorably to odanacatib. Identification of genetic markers that associate with musculoskeletal disease, e.g., osteoporosis, will be achieved by using both the biased approach of drug-metabolizing genes and unbiased genome wide scans. The primary analysis will be cross-sectional using the baseline clinical traits, while the secondary analysis will be longitudinal, using multiple regression models across all patients, in each of the two study arms separately, treating the genotypes as the independent variables and the phenotypes being the dependant variables. New composite measures of musculoskeletal disease, e.g., osteoporosis, are envisioned to be developed that combine multiple measures of bone and muscle health, e.g., BMD, LBM, bone quality, muscle quality, circulating protein markers, and genotype) and utilizes this new composite measure in both the cross-sectional case control studies as well as the longitudinal studies described above. Although a particular composite measure has not been chosen as of yet, one potential method of combining data is shown below. For example, a regression analysis can be conducted by simply treating the three measures (BMD, bone formation markers and bone quality [by biopsy or advanced imaging modality]) as elements of the mixed effect model, similar to the way repeated measures are dealt with, and such model can directly test if genotype is associated with any of these measures singly or through composite crossed terms of these measures. Given the evolving nature of the statistical methodology on GWAS, and biological understanding of musculoskeletal disease, any changes to the statistical methodology and analyses would be outlined and documented in the results memorandum.

Product: MK-0822

52

Protocol/Amendment No.: 018-04

Summary of Efficacy Analyses:

A summary of the efficacy analyses performed in this study is in Table 3-10.

Table 3-10
 Efficacy Analyses

Efficacy Endpoint	Statistical Method	Analysis Approach	Additional remark
Morphometric Vertebral Fractures			
Time to first fracture	Life-table estimates for each time point	FAS + PP	PP only if >10% PVs.
Time to first fracture	Interval censored analysis (cloglog model)	FAS + PP	PP only if >10% PVs.
Time to first fracture	Summary of number (%) of patients with a fracture up to each time point	FAS + PP	PP only if >10% PVs.
Number of fractures	Summary of number (%) patients with 0, 1, 2, >2 fractures	FAS	
Clinical Fractures (Hip, Non-vertebral and Vertebral)			
Time to first fracture	Kaplan-Meier curve and estimates for each time point	FAS + PP	PP only if >10% PVs.
Time to first fracture	Cox proportional hazards model	FAS + PP	PP only if >10% PVs.
Number of fractures	Summary of number (%) patients with 0, 1, 2, >2 fractures	FAS	
Stature			
Change from baseline at each time point	Summary table and line plot over time.	FAS	
Stature loss of >1 cm	Summary of number (%) patients and logistic model	FAS	
Rate of stature loss	Mixed model with fixed effects for treatment, stratum, region, treatment-time and random intercept and slope.	FAS	
Bone Mineral Density Endpoints			
Percent change from baseline at all time points.	Summary table.	FAS	
Percent change from baseline at all time points.	Longitudinal approach and line plot of LS means over time	FAS	
Bone Biopsy Endpoints			
Bone biopsy measurements	Summary table.	FAS	

Product: MK-0822

54

Protocol/Amendment No.: 018-04

Efficacy Analyses (Cont.)

Efficacy Endpoint	Statistical Method	Analysis Approach	Additional remark
Qualitative abnormality [†]	Summary of number (%) of patients	FAS	
Biochemical Markers of Bone Resorption and Bone Formation			
Log-transformed fraction from baseline	Summary table of geometric mean percent change from baseline.	PP	
Log-transformed fraction from baseline	Longitudinal model and line plot of LS mean over time.	PP	Testing only for resorption markers.
Indices of Calcium and Mineral Homeostasis			
Log-transformed fraction from baseline	Summary table of geometric mean percent change from baseline.	PP	
Major Cardiovascular and Cerebrovascular Events			
Time to first event	Kaplan-Meier curve and estimates for each time point	FAS	
Health Resource Utilization Questionnaire			
Patients who received medical care and type of care	Summary of number (%) of patients overall and per time point. Summary of event-rate per type of medical care visit. Summary of number (%) of patients by type of fracture.	FAS	
Meal Questionnaire			
Meal questionnaire items	Summary of number (%) of patients per time point	FAS	Only performed for “Lead Cohort”.
FAS= Full Analysis Set; PP= Per Protocol; PV= Protocol Violator [†] Incidence of qualitative abnormalities on bone biopsies will be considered a safety endpoint.			

Product: MK-0822

55

Protocol/Amendment No.: 018-04

